### 3.2.3 Turoctocog alfa pegol clinical data

In accordance with the European Medicines Agency (EMA) guidelines and other regulatory advices the clinical programme for N8-GP was initiated with a first-human-dose trial to document the essential pharmacokinetic characteristics of the product and to obtain initial safety information.

In the first human dose trial NN7088-3776 (pathfinder1), a single dose of N8-GP (25 IU/kg body weight (BW), 50 IU/kg BW or 75 IU/kg BW) was administered to 26 adult previously treated patients with severe haemophilia A being in a non-bleeding state. N8-GP was well-tolerated and the safety profile of N8-GP appeared similar to that of marketed FVIII products. The mean half-life of N8-GP was shown to be 18.4 hours, corresponding to a 1.6-fold prolongation compared to the half-life of un-modified FVIII products (patient's previous product including rFVIII and pdFVIII).

Four clinical trials investigating the safety and efficacy of N8-GP are on-going – a pivotal phase 3 trial NN7088-3859 (pathfinder2) which includes an extension phase divided in two parts, part 1 and part 2, a phase 3 surgery trial NN7088-3860 (pathfinder3), a paediatric phase 3 trial NN7088-3885 (pathfinder5), and a previously untreated patients phase 3 trial NN7088-3908 (pathfinder6).

The pivotal part of trial NN7088-3859 (pathfinder2) in adolescents and adults documented the safety and efficacy of a prophylactic regimen with 50 IU/Kg BW of N8-GP given every four days. The annualised bleeding rate (ABR) was estimated to 3.70 and the median ABR rate was estimated to 1.33. The estimated success rate for treatment of all bleeds was 84.2% and the haemostatic effect of N8-GP was confirmed. The extension phase part 2 is on-going.

In the trial NN7088-3860 (pathfinder3) the efficacy and safety of N8-GP during major surgical procedures in patients with severe haemophilia A is evaluated. The haemostatic effect of N8-GP during surgery for the first interim was demonstrated. All surgeries were effectively performed with N8-GP. The haemostatic effect of N8-GP was rated as “excellent” or “good” in 17 out of 18 surgeries (94.4%), and as “moderate” in 1 surgery. The haemostatic effect of N8-GP during the post-operative period, Days 1–14, was also demonstrated. No FVIII inhibitory antibodies were detected, no thromboembolic events occurred and no other clinically significant safety issues were identified. The trial is on-going.

Protocol  
NN7088-4410

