## 5.4 Scientific rationale for trial design

Historically, the aim of prophylactic treatment in severe haemophilia A has been to maintain at least a 0.01 IU/mL (1 IU/dL) FVIII activity level. However, recent studies have suggested that the maintenance of higher FVIII activity levels is desirable in order to further reduce and potentially even eliminate the risk of spontaneous bleeding episodes by converting patients from a severe to a mild haemophilia A phenotype .

Apart from investigating the overall safety of N8-GP during continuous use, the purpose of this trial is to demonstrate that N8-GP can convert patients to a milder bleeding phenotype, and to evaluate the clinical benefit of maintaining higher FVIII trough levels with FVIII replacement. To achieve this, there is an option to intensify the N8-GP dosing regimen from every four days dosing (previous regimen in NN7088-3859 (pathfinder2)) to twice weekly or three times weekly.

In addition, the trial aims to provide additional clinical outcome data – e.g. target joint status and clinical safety data in patients with haemophilia A after on-going N8-GP treatment.

Protocol  
NN7088-4410

~~CONFIDENTIAL~~

Date:  
Version:  
Status:  
Page:

18 June 2019  
2.0  
Final  
19 of 86

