### 9.8.8 Immunogenicity assessments

#### 9.8.8.1 Evaluation of FVIII inhibitors and antibodies

Blood samples will be analysed for antibodies according to the flowchart see section [2](#):

- FVIII inhibitors

 The trough level is defined as the lowest level of FVIII measure immediately prior to doing and reported as IU/mL

 Recovery level is the FVIII level 30 min after trial product administration relative to the dose administered and will be reported as (IU/mL)/(U/kg)

Protocol  
NN7088-4410

~~CONFIDENTIAL~~

Date:  
Version:  
Status:  
Page:

18 June 2019  
2.0  
Final  
49 of 86

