#### **Pre-dose FVIII activity levels on N8-GP prophylaxis**

The following rules will be implemented for FVIII pre-dose and post-dose activity to ensure data representing steady-state on a given treatment regimen:

- FVIII activity data prior to the 4th prophylaxis dose will be excluded for each switch in treatment regimen
- FVIII activity data will be excluded if post-dose activity is  $\leq$  pre-dose FVIII activity
- FVIII activity data will be excluded if post-dose sample is taken more than 90 minutes after dosing
- FVIII activity results will be excluded for plasma samples defrosted during transit.

Protocol  
NN7088-4410

~~CONFIDENTIAL~~

Date:  
Version:  
Status:  
Page:

18 June 2019  
2.0  
Final  
57 of 86

Novo Nordisk

The pre-dose FVIII activity levels will be modelled to get an estimate of the pre-dose level for N8-GP at steady-state. The model will be a mixed model on the logarithmic plasma activity levels with age as a factor and patient as a random effect. Separate modelling will be performed for each treatment regimen. Plasma concentrations below lower limit of quantification (LLOQ) will be set to half the value of the LLOQ. The estimated pre-dose FVIII level will be presented together with the 95% confidence intervals.

A sensitivity analysis will be performed including all activity results except activities measured in relation to the first 4 prophylaxis doses after switch of treatment regimen.

Pre-dose activity will furthermore be summarised by visit and treatment regimen.

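### If once-weekly samples are true 7-day troughs and the LLOQ is about 0.5 to 1 IU/dL or more, LLOQ/2 substitution would overstate the once-weekly FVIII trough and its precision

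*Protocol*

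**What the plan says.** Pre-dose FVIII activity is a supportive secondary endpoint. Protocol 10.3.2.1 and SAP 2.3.2.1 describe the same analysis:

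- Model: "The model will be a mixed model on the logarithmic plasma activity levels with age as a factor and patient as a random effect".
- Regimens: "Separate modelling will be performed for each treatment regimen". The once-weekly estimate therefore borrows nothing from the other two.
- Low values: "Plasma concentrations below lower limit of quantification (LLOQ) will be set to half the value of the LLOQ".
- Reporting: "The estimated pre-dose FVIII level will be presented together with the 95% confidence intervals".
- Sensitivity: "A sensitivity analysis will be performed including all activity results except activities measured in relation to the first 4 prophylaxis doses" after a switch of regimen. This changes which samples are used and leaves the LLOQ rule as it is.

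Neither document gives the LLOQ or plans to report the share of values below it.

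Two places bear on when the sample is drawn. Footnote 2, attached to Protocol 9.8.7.1, defines the trough as the "lowest level of FVIII measure immediately prior to doing" (a misprint for dosing). Flowchart footnote d asks for FVIII activity sampling to follow a wash-out of roughly 3 days. The exclusion rules in 10.3.2.1 set no limit on the time since the previous dose.

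**The concern.** Once weekly is the regimen with the longest interval, 168 h. Protocol 3.2.3 reports for the first-human-dose trial: "The mean half-life of N8-GP was shown to be 18.4 hours". That makes 168/18.4 = 9.1 half-lives between doses. Patients have severe disease with endogenous FVIII below 1%, so endogenous activity would not lift the level clear of a limit near 1 IU/dL.

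If most values fall below the LLOQ, replacing each with the same number does two things on the log scale. It pulls the estimate towards LLOQ/2, and it removes real variation between and within patients, which shortens the interval. Protocol 5.4 gives as one aim "to evaluate the clinical benefit of maintaining higher FVIII trough levels with FVIII replacement", so a reader is likely to set the regimens' trough estimates side by side.

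**Working it through.** The documents give no trough, LLOQ or share below LLOQ for this endpoint, so there is no stated figure to reproduce.

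**Inputs from the documents.** Mean half-life 18.4 h (Protocol 3.2.3). Doses: 75 IU/kg once weekly, 50 IU/kg twice weekly from age 12, 50 IU/kg three times weekly (7.1.1). Mean intervals are 168, 84 and 56 h.

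**Assumed inputs.** Incremental recovery 2.0 to 3.0 IU/dL per IU/kg, half-life CV 15 to 35%, LLOQ 0.3 to 3 IU/dL.

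**Step 1: typical level.** With one-compartment kinetics at steady state, level at time t = dose × recovery × 2^(−t/18.4) / (1 − 2^(−interval/18.4)). For once weekly at 168 h and recovery 2.5: 75 × 2.5 × 0.001784 / 0.998 = 0.34 IU/dL.

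| Regimen and sampling time | Recovery 2.0 | 2.5 | 3.0 |
|---|---|---|---|
| Once weekly, 168 h | 0.27 | 0.34 | 0.40 |
| Once weekly, 72 h | 10.0 | 12.5 | 15.0 |
| Twice weekly, 84 h | 4.4 | 5.5 | 6.6 |
| Three times weekly, 56 h | 13.8 | 17.3 | 20.7 |

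The typical 7-day trough lies below any LLOQ of 0.5 IU/dL or more. The 72 h level is 2^(96/18.4) = 37 times higher.

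**Step 2: effect of the substitution.** Simulated log levels, 400,000 draws: log-normal half-life with mean 18.4 h, recovery 2.5 with log SD 0.2, residual log SD 0.25, every value below the LLOQ replaced by LLOQ/2. As a check on the true geometric mean (GM), ln(GM) ≈ ln(187.5) − (168 × ln 2/18.4) × (1 + CV²), which gives 0.29, 0.23 and 0.15 IU/dL for CV 15, 25 and 35%. The last digit carries simulation error.

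| Half-life CV | LLOQ (IU/dL) | Below LLOQ | Estimate ÷ true GM | Log SD ÷ true log SD |
|---|---|---|---|---|
| 15% | 0.5 | 69% | 1.3 | 0.62 |
| 25% | 0.5 | 65% | 1.9 | 0.50 |
| 35% | 0.5 | 64% | 3.2 | 0.41 |
| 15% | 1 | 90% | 1.9 | 0.34 |
| 25% | 1 | 81% | 2.9 | 0.34 |
| 35% | 1 | 76% | 4.7 | 0.31 |

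**Step 3: where the effect fades.**

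- LLOQ 0.3, half-life 18.4 h, CV 15%: 49% below, ratio 1.09.
- Mean half-life 22 h, CV 15%: ratio 0.98 at LLOQ 0.3 to 0.5, and 1.05 at LLOQ 1.
- Once-weekly samples at 72 h: 0 to 15% below at any LLOQ up to 3, ratio 0.99 to 1.02.
- Twice and three times weekly over the whole grid: ratio 0.94 to 1.17.

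**Step 4: the interval, and whether a censored model helps.** 60 simulated trials per case, assuming 20 patients with 5 samples each, true GM 0.33 IU/dL and within-patient log SD 0.35. Half-widths are on the log scale.

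| Between-patient log SD | LLOQ | LLOQ/2: GM, half-width, coverage | Left-censored: GM, half-width, coverage |
|---|---|---|---|
| 1.2 | 0.5 | 0.47, 0.38, 68% | 0.35, 0.62, 93% |
| 1.2 | 1 | 0.65, 0.24, 0% | 0.35, 0.79, 86% (57 of 60 fits usable) |
| 0.6 | 0.5 | 0.34, 0.20, 97% | 0.33, 0.32, 90% |

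With large spread the nominal 95% interval fails under substitution. With small spread and LLOQ 0.5 it happens to do well.

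**The case against.** The strongest reply is that every input that decides the matter is missing from the documents: LLOQ, recovery, half-life spread and the once-weekly sampling time. A reader might infer that the once-weekly trough must be an artefact of the assay. The documents do not support that. Protocol 3.2.1 does describe FVIII below 1% as not measurable, but it is speaking of endogenous levels in severe disease and does not state an assay limit. The 18.4 h figure is a mean from a single-dose trial in 26 adults. Patients already on once weekly were selected for few bleeds (5.5) and may clear more slowly, which is itself an inference. Under those conditions, or with a low LLOQ and small spread, bias is near zero or slightly downward. All of this stands, and it is why the point is conditional.

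Flowchart footnote d also stands. At about 3 days almost nothing is censored. But that does not settle matters for the plan: the sample would then not be a 7-day trough, and no exclusion rule separates the two cases.

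A reader might further infer that the trial's case depends on this estimate, or that young children's results are distorted. Neither follows. The primary endpoint is adverse events, trough is absent from the synopsis's key secondary endpoints, and no between-regimen trough contrast is planned. For children, the protocol says only that clearance is expected to be higher and gives no half-life.

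Finally, the censored model is no cure-all: at LLOQ 1 its coverage was 86%, and it is barely identified when nearly every value is censored.

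**Conclusion.** The concern holds conditionally. If once-weekly pre-dose samples are taken at about 7 days and the LLOQ is about 0.5 to 1 IU/dL or more, most once-weekly values would be replaced by a constant. At LLOQ 0.5 to 1, the estimated trough would be about 1.3 to 5 times too high with too narrow a 95% confidence interval. This rests on the 18.4 h half-life, an assumed CV of 15 to 35%, assumed recovery of 2.5 and one-compartment kinetics. The other two regimens are little affected. Outside those conditions the effect can be small or absent. The weakness in the plan is that one fixed substitution is used, nothing tests it, and the report would not show which situation applied. As this is a descriptive secondary endpoint, the change is a worthwhile, inexpensive improvement and does not threaten the trial's main conclusions.

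**What to change.** Amend the SAP before database lock:

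1. State the LLOQ, and report the percentage of pre-dose values below it by regimen and age group.
2. Fit the same mixed model with values below the LLOQ treated as left-censored, and present it alongside the LLOQ/2 result.
3. Pre-specify a fallback: where nearly all values in a group are censored, report the percentage below the LLOQ and give the trough as <LLOQ, with no model estimate.
4. Summarise the actual time since the previous dose for once-weekly pre-dose samples, and reconcile flowchart footnote d with the trough definition in footnote 2 to Protocol 9.8.7.1.

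The cost is SAP wording and some programming on data already planned for collection. The downside is a slightly more complex model that may need simpler random effects, or may not converge, under heavy censoring.

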#### **Change in joint health status from start to end of trial**

Target joint status is assessed at inclusion in trial. For intervals of 12 months, the number of baseline target joints with 0, 1, 2, ... number of bleeds is presented.

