### 3 Introduction

#### 3.1 Trial rationale

The rationale for performing this trial is to allow the continued evaluation of the safety and efficacy of turoctocog alfa pegol (N8-GP) in order to obtain additional data on long-term use of N8-GP. Introducing a twice or three times weekly prophylactic dosing regimen to the majority of patients is intended to show potential improvement in clinical outcomes by converting patients to a milder bleeding phenotype. Joint health and target joints will be assessed and evaluated at inclusion and at end of trial (EoT).

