### 9.5.2 Target Joint assessment

A joint status including target joints must be assessed.

- Joint status based on the Haemophilia Joint Health Score, see section [9.5.2.1](#)
- Current target joint(s), including number of spontaneous bleeding episodes for the last 12 months in each current target joint. - A target joint is defined as a joint with three or more spontaneous bleeding episodes within a consecutive period of 6 months. When there has been no spontaneous bleeding episode in the joint for 12 months, it is no longer considered a target joint.

Clinically significant findings present at screening should be recorded as concomitant illness and during the trial as AEs. Any changes in the examination which fulfil the criteria of an AE (see section [9.6](#)) or an update to concomitant illness (see section [9.8](#)) must be recorded as such.

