1.1 Trial information

In the following, a brief description of the trial is presented. Please go to the protocol for further details.

Rationale:

The rationale for performing this trial is to allow the continued evaluation of the safety and efficacy of turoctocog alfa pegol in order to obtain additional data on long-term use. Introducing a twice or three times weekly prophylactic dosing regimen to the majority of patients is intended to show potential improvement in clinical outcomes by converting patients to a milder bleeding phenotype. Joint health and target joints will be assessed and evaluated at inclusion and at end of trial.

Objectives and endpoints:

Primary objective

To investigate the safety of turoctocog alfa pegol during continuous use for prevention and treatment of bleeding episodes of previously turoctocog alfa pegol treated severe haemophilia A patients.

Secondary objectives

To investigate the following in severe haemophilia A patients previously treated with turoctocog alfa pegol

- Development of FVIII inhibitors
- Efficacy of turoctocog alfa pegol prophylaxis
- Haemostatic efficacy of turoctocog alfa pegol when used for treatment of bleeds

Overall design:

This phase 3 trial is a multi-centre, multi-national, open-label, non-randomised trial evaluating safety and efficacy of turoctocog alfa pegol during prophylaxis treatment and treatment of bleeds. There will be three turoctocog alfa pegol treatment arms (dosing once weekly, twice weekly, and three times weekly) and no comparator.

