Change in joint health status from start to end of trial

Target joint status is assessed at inclusion in trial. For intervals of 12 months, the number of baseline target joints with 0, 1, 2,... number of bleeds is presented.

Haemostatic response during major surgical interventions

The endpoint of assessment of haemostatic effect during major surgical intervention (excellent, good, moderate or none) will be summarised and listed.

Change from baseline till end of trial in treatment satisfaction (Hemo-SAT)

Data will be scored according to established scoring algorithms (where applicable) and changes from first assessment (at screening/V1) to last assessment (at EoT visit) will be summarised and listed using descriptive statistics. Further analysis will be performed separately by Novo Nordisk Health Economics Department.

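### The only planned target-joint table follows joints that were target joints at baseline, so it cannot show new target joints or the total at end of trial

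*Protocol*

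**What the plan says.** Under the endpoint on change in joint health status, protocol 10.3.2.1 first says that "Target joint status is assessed at inclusion in trial". It then gives its single output: "For intervals of 12 months, the number of baseline target joints" is broken down by number of bleeds (0, 1, 2 and so on). SAP 2.3.2.1 repeats this and adds nothing.

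The stated intention is wider. Protocol 3.1 says "Joint health and target joints will be assessed and evaluated at inclusion and at end of trial (EoT"), and the protocol synopsis and SAP 1.1 say the same. Protocol 5.4 names target joint status among the clinical outcomes the trial aims to provide.

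Protocol 9.5.2 defines the status in both directions. For entry: "A target joint is defined as a joint with three or more spontaneous bleeding episodes within a consecutive period of 6 months". For exit: "When there has been no spontaneous bleeding episode in the joint for 12 months, it is no longer considered a target joint".

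**The concern.** The denominator is fixed at inclusion. A baseline target joint can go quiet or keep bleeding, and either would be visible. A joint that first meets the 9.5.2 definition in month 10 appears nowhere, and no planned output gives the number of target joints at end of trial. The evaluation promised for that time point is therefore missing for target-joint status.

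Selection makes this more than a missing row. A joint is in the table because it had a cluster of bleeds and has not since gone 12 months without a spontaneous one. If bleeding varies by chance around a stable rate, some of these joints will bleed less afterwards whatever the treatment does, while others cross the threshold unseen. The trial has no comparator, so nothing within this table separates that effect from benefit.

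At stake is the reading of the trial's aim of showing a milder bleeding phenotype (protocol 5.4). A table confined to joints that were bad at entry could be taken as support for that aim when the number of target joints has not moved.

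**Working it through.** The plan states no figure for target joints, so there is none to reproduce. The check asks what the planned table would show, and what it would omit, if treatment had no effect.

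**Inputs from the documents**
- 170 patients expected on trial product (protocol 5.2).
- 104 weeks of treatment (5.1), so two 12-month intervals.
- Entry and exit rules from 9.5.2.

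**Assumptions**
- Six joints per patient: two elbows, two knees, two ankles. Section 9.5.2.1 names these joint types; taking six is an assumption.
- Each joint has a constant spontaneous-bleed rate λ, gamma-distributed across joints with mean r and shape k. Bleeds over time T are Poisson(λT).
- A long run-in, so that the number of target joints is stable at entry.
- No early completion, and every bleed counts.

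**Rules applied.** Status starts at a third bleed within 0.5 years and ends after 1.0 year without a bleed. The identity to check is: total at end = baseline − resolved + new and still present at end. Joints that are new at any time exceed those still present at end, because some new ones resolve again.

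**Results, scaled to 170 patients**

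| r per joint-year (shape) | Baseline | No longer target joints at 2 years | Ever new | New and present at end | Total at end |
|---|---|---|---|---|---|
| 0.3 (0.3) | about 36 | about 17 | about 23 | about 18 | about 37 |
| 0.15 (0.2) | about 12 | about 7 | about 10 | 7 to 8 | about 13 |
| 0.05 (0.2) | about 1 | – | about 1 | – | – |

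First row: 36 − 17 + 18 = 37. The second row agrees within rounding: 12 − 7 + 7 or 8 = 12 or 13.

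**What the planned table would show in the first row.** In year 1, about 7 of 36 joints (20%) have no bleeds, about 12 (32%) have three or more, and the remaining 36 − 7 − 12 = 17 have one or two. The roughly 23 ever-new joints are not shown.

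**Are the rates plausible?** 0.3 × 6 = 1.8 spontaneous joint bleeds per patient-year. Protocol 3.2.3 gives annualised rates for all bleeds of 3.70 (adolescents and adults, pathfinder2) and 2.13 (children, pathfinder5). The first row therefore makes spontaneous joint bleeds 1.8/3.70 = 49% and 1.8/2.13 = 85% of all bleeds, which is high for children. The other rows correspond to 0.15 × 6 = 0.9 and 0.05 × 6 = 0.3 per patient-year.

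**Wider grid.** With 1.0, 2.0 or 3.7 spontaneous joint bleeds per patient-year and shapes 0.1, 0.3 and 1.0, the nine scenarios give:
- 7% to 55% of baseline target joints with no bleeds in a 12-month interval;
- 3% to 67% with three or more in year 1;
- 19% to 89% no longer target joints at 24 months.

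New target joints replace them almost one for one. At 2.0 per patient-year and shape 0.3, 19.4 are lost and 19.4 gained, and the total stays at 43.6.

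**The case against.** A reader might infer that the table can only show improvement, or that it would report resolution even with no change. The documents do not support that. The output is a full distribution of bleed counts, so persistent bleeding is as visible as its absence. In the first scenario about 80% of baseline joints visibly still bleed in each interval. The figure of 17 joints losing the status comes from a derivation the plan does not contain; the planned table would show about 7 at zero. Even that column is only a proxy for resolution, because the output says bleeds without restricting them to spontaneous ones.

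Three further objections carry weight.
- **Importance.** Section 4.2.2 lists no target-joint endpoint. The endpoint served here is based on the Haemophilia Joint Health Score, and the table is descriptive, in an uncontrolled trial whose primary objective is safety. That no analysis of the score is planned is a separate and arguably larger gap.
- **Partial coverage.** Bleeding rates are estimated by location and by cause, and clinically significant joint findings during the trial are recorded as adverse events. Bleeding in other joints is therefore not ignored, but neither route yields a count of target joints.
- **Assumed rates.** The counts depend wholly on them, and at the low end there is almost nothing to count.

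These points limit the weight of the concern. They do not supply the missing counts.

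**Conclusion.** The concern holds in a limited form. The planned table can show whether baseline target joints keep bleeding. It cannot show target joints that develop during the trial or the total at end of trial, and no other planned output does. That falls short of the documents' own statement that target joints are evaluated at both time points. Because of how baseline joints are selected, the table can suggest improvement when the total is unchanged.

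The size is uncertain. Across the three illustrated rates the number of ever-new joints runs from about 1 to about 23, under constant rates, gamma variation between joints, six joints per patient and no treatment effect. The direction does not depend on those choices as long as bleeding fluctuates by chance. If exactly the same joints went on bleeding, the table would show that. The omission is worth correcting because the correction is cheap, but it does not touch the primary objective.

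**What to change.** Keep the planned table. In protocol 10.3.2.1 and SAP 2.3.2.1, add one that applies the 9.5.2 definition to every joint, using the bleed date, location and cause already recorded under 9.5.1 and the bleed history transferred from the earlier trials. Report target joints at entry, resolved, newly developed at any time, and present at end of trial.

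The text should also:
- state that spontaneous bleeds determine status, as 9.5.2 has it;
- state whether untreated bleeds count, since 9.5.1 records them but 10.3.2 restricts bleed endpoints to those treated with N8-GP;
- show patients who complete early on commercial availability (5.2.1) with their observation time, since a short follow-up may not allow 12 bleed-free months to accrue.

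A split by regimen is optional, because the counts may be very small.

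The cost is one derivation and one table from data already collected. The result may look less favourable than the baseline-only table.
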